**2021**

## Introduction

Advanced maternal age (AMA) is mostly defined as a pregnancy in women  $\geq 35$  years of age or more during their pregnancy or time of delivery (1). It grows trending in high-income countries, which is most commonly seen in older primigravida women who delay child bearing by life style choice or due to underlying subfertility, but also includes multiparous women continuing childbearing. Approximately 18% of all united states birth in 2018 were to women with advanced maternal age compare with approximately 5% before, much of this shift due to delayed first births, the rate of first births increased seven-fold among women aged 35 to 39 y and five-fold among women aged 40 to 44 y between 1985 and 2018 (2).

In England, the incidence of births to women aged 35y increased from 6% to 20% at 2013. Pregnancy at advanced maternal age is associated with different adverse neonatal outcomes. It is associated with stillbirth and also complicated by intrauterine fetal death (IUFD) and neonatal death (3 & 4). Advanced maternal age is reported to be associated with a range of pregnancy complications including: fetal growth restriction (FGR), preeclampsia (PE), placental abruption, pre-term birth (PTB) and stillbirth (5).

Perinatal adverse outcomes like preterm birth, early neonatal death, low birth weight, neonatal intensive care unit (NICU) admission and APGAR score of less than seven at five minutes are significantly associated with pregnancy at advanced maternal age (6). The adverse outcomes result from inadequate cardiovascular adaptation during pregnancy, which impedes the hemodynamic changes for supporting the fetus (7). This may explain occurrence of intrauterine growth restriction and placental abruption at advanced maternal age (8).

Early pregnancy outcomes associated with advanced maternal age include: Ectopic pregnancy which increase a four- to eight-fold in women more 35 years increasing maternal mortality and morbidity (9). Epidemiological studies show an association between advanced maternal and paternal ages and the risk of autism spectrum disorders in the offspring, also advanced maternal age is a risk factor for congenital malformation and Down syndrome (10).

Risk of spontaneous abortion between 6 to 14 weeks of pregnancy increased with increasing maternal age (11). Late pregnancy outcomes including Gestational DM and preeclampsia which increasing up to 10% in women more 40 years of age and higher up to 35% in women more than 50 years of age which may cause intra uterine growth retardation and stillbirth (12).

Advanced maternal age is also linked to a higher prevalence of placenta praevia and placental abruption, both of which cause bleeding in late pregnancy (after about 20 weeks) especially in multipara (13). Women more than 40 years of age showed an eight-fold increased risk of amniotic fluid embolism due to increased incidence of caesarian section and a three-fold increased risk of obstetric shock compared with women age 25–29 years (14).

According to the royal college of obstetricians and gynecologists, the optimum period for child bearing is between 20 and 35 years of age to decrease maternal and neonatal complications (15).

### **Aim of work**

This study to evaluate the effect of advanced maternal age on the outcomes of pregnancy which include: maternal, obstetric, fetal and perinatal outcomes.

## **Patient and methods**

### **Study Design & Area:**

- A prospective cohort study of pregnant women recruited from Department of Obstetrics and Gynecology, Mansoura University Hospitals during **June** 2021 until **June** 2022 and may be extended if needed.
- The hospital operates Antenatal clinics six hours every day except Friday.
- Mansoura University Hospital is Referral teaching hospital, located in Mansoura, Egypt.

### **Study population:**

The study group will be represented by 50 primigravida women aged 35y or more during their pregnancy and the control group will be represented by 50 primigravida women aged 20-34 y during their pregnancy till the time of delivery.

#### **A. Inclusion criteria:**

- Primigravida Women with singleton pregnancies aged 20 to 34 years in control group and aged 35 y or more in case group, natural conception or with using ART, who seeking for routine antenatal care to the university hospital and who will accept the study protocol.

#### **B. Exclusion criteria:**

- Patients aged less than 20 y will be excluded from the study.
- Patients with medical disorders (antiphospholipid syndrome, chronic hypertension, pre-existing diabetes, autoimmune diseases, thrombo-embolic disease).
- Multipara.

## Sample size

Sample size was calculated by PASS 15 Power Analysis and Sample Size Software (2017). NCSS, LLC. Kaysville, Utah, USA, [ncss.com/software/pass](http://ncss.com/software/pass).

Based on previous studies including Yogev et al. (2010), the authors hypothesize an overall poor outcome in 20% of young pregnant group vs. 60% in elderly pregnant group with a prevalence of elderly pregnant ladies of 25% vs. 75% of young pregnant ladies.

A logistic regression of a binary response variable (Y) on a binary independent variable (X) with a sample size (N) of 80 observations (of which 50% are in the group X=0 [40 young pregnant ladies] and 50% are in the group X=1 [40 elderly pregnant ladies]) achieves 94% power at a 0.050 significance level to detect a change in Prob (Y=1) from the baseline value of 0.200 to 0.600. This change corresponds to an odds ratio of 6.000. A two-sided Wald test is used.

Considering a possible dropout rate (DR) of 20%, the expected number of dropouts will be 20, and the dropout-inflated enrollment sample size (N') will be 100 participants (50 young, and 50 elderly) where  $N' = N / (1 - DR)$ .

- We will have 2 groups: the **first** group will be represented by 50 women aged 35 y or more and the **second** group will be represented by 50 women aged from 20 to 34 y.
- **The first group** will be also divided into 2 subgroups: group (1A) aged from 35y to 40 y, the group (1B) aged above 40 y and we will compare between the outcomes in the 2 groups which include maternal, obstetric, fetal and perinatal outcomes.
- We will also compare between those with spontaneous pregnancy and those with ART.

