### **III. Investigations:**

- All pregnant women will undergo routine investigations at the first antenatal visit which include: CBC, RH grouping, blood grouping, urine analysis, fasting and postprandial blood glucose.

-All pregnant women will be screened for gestational diabetes mellitus (GDM) with a 50-g oral glucose challenge test between 24 and 28 weeks of gestation. Women with abnormal glucose challenge test (140 mg/dL) will undergo a 3-hour oral glucose tolerance test with a 100-g oral glucose load. The diagnosis of GDM will be made when levels of blood glucose are fasting plasma glucose above 95 mg/dL, 1 hour postprandial above 130-140 mg/dL, and 2 hours postprandial above 120mg/dL according to The American College of Obstetricians and Gynecologists (ACOG) recommendations (17).

- All pregnant women will undergo a monthly ultrasound examination until delivery.

- All obstetrical and clinical data will be recorded and collected in an appropriate database.

-Obstetric outcomes will be recorded regarding pregnancy induced hypertension, gestational diabetes mellitus (GDM), anemia, antepartum hemorrhage, oligohydraminos or polyhydraminos, obtetretic shock and intrapartum hemorrhage.

-Maternal outcomes will be recorded regarding mode of delivery “cesarean or vaginal delivery”, premature rupture of membranes, preterm birth which is defined as delivery of an infant before 37 weeks of gestation and will be classified into late preterm (from 34 to less than 37 weeks of gestation) and early preterm birth (delivery from 28 to 34 weeks of gestation), obstructed labor and prolonged labor.

-Fetal outcomes will be recorded regarding congenital malformations, intrauterine growth restriction, intrauterine fetal death and stillbirth.

- Perinatal outcomes will be recorded regarding birth weight which will be classified into low birth weight (less than 2500 g), very low birth weight (less than 1500 g) and macrosomia (more than 4000 g), birth asphyxia, meconium aspiration syndrome, NICU admission, neonatal hypoglycemia, Hyperbilirubinemia, 5-Min Apgar score less than 7 and neonatal death.

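### The 94% power is for an overall poor outcome that the plan never defines, and no primary outcome is named

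*Combined protocol and SAP*

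**What the plan says.** The Sample size section hypothesizes that "the authors hypothesize an overall poor outcome in 20% of young pregnant group vs. 60% in elderly pregnant group". It models this as a logistic regression of a binary response on age group, with 40 women per group and a two-sided Wald test, and says that the design "achieves 94% power at a 0.050 significance level to detect a change in Prob (Y=1) from the baseline value of 0.200 to 0.600". Allowing for 20% dropout, 50 women per group are enrolled. The rates are introduced with "Based on previous studies including", followed by a single 2010 study cited by author and year.

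Elsewhere the outcomes are described differently:

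- The Aim of work is to "evaluate the effect of advanced maternal age on the outcomes of pregnancy which include: maternal, obstetric, fetal and perinatal outcomes". It names four domains and ranks none.
- The Investigations section lists individual outcomes under the same four domains, starting with "Obstetric outcomes will be recorded regarding pregnancy induced hypertension, gestational diabetes mellitus (GDM), anemia, antepartum hemorrhage". It gives no composite.
- The Sample size section adds that "we will compare between the outcomes in the 2 groups which include maternal, obstetric, fetal and perinatal outcomes", in the bullet that splits the older women into 1A and 1B, and then that "We will also compare between those with spontaneous pregnancy and those with ART".
- The Statistical analysis section suggests chi-square for categorical data. It names no primary outcome or primary analysis, and mentions neither the overall poor outcome nor logistic regression.

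**The concern.** A power statement belongs to one endpoint, one contrast and one test. Here the contrast and the test are given, but the endpoint is only a label. The text available for review gives no list of events, no rule for combining them and no time window.

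Two things are at stake. First, a reader who sees 94% power may carry it over to the listed outcomes and take a null result on one of them as evidence that age makes no difference, when the study may have had little chance of detecting one. Second, with no fixed list, the components of the composite could be chosen after the outcomes are known. A result on a composite built that way would not carry its nominal 5% error rate, and this cannot be credibly repaired afterwards.

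**Working it through.** **1. Reproduce the stated power.** Inputs from the Sample size section: p0 = 0.20, p1 = 0.60, n = 40 per group, two-sided 0.05.

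- Odds ratio = (0.60/0.40)/(0.20/0.80) = 6.0, as stated.
- Standard error of the log odds ratio = √[1/(40×0.2×0.8) + 1/(40×0.6×0.4)] = √(0.15625 + 0.10417) = 0.5103.
- Power = Φ(ln 6/0.5103 − 1.960) = Φ(3.511 − 1.960) = Φ(1.551) = 0.9396.
- Enrolment = 80/(1 − 0.20) = 100, as stated.

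For the same rates, exact enumeration gives 0.968 for the uncorrected chi-square test and 0.947 for Fisher's exact test. The calculation is sound for its inputs.

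**2. Look for the endpoint.** The overall poor outcome occurs only in the Sample size section. The aim, the recorded outcomes and the statistical analysis do not mention it. The reference list has 17 numbered entries, none dated 2010, so the sizing study is not among them.

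**3. Count what is listed.** Taken as written, there are 7 obstetric + 5 maternal + 4 fetal + 8 perinatal = 24 outcomes. Separating oligohydramnios from polyhydramnios, late from early preterm birth, and the three birth-weight classes gives 8 + 6 + 4 + 10 = 28. None is marked as primary.

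**4. Ask what power a single outcome would have.** The rates below are assumptions chosen to show the range. The pooled two-proportion formula is power = Φ{[d − 1.960√(2p̄(1−p̄)/n)] / √[(p0(1−p0) + p1(1−p1))/n]}, where d = p1 − p0, p̄ is the mean of the two rates and n = 40.

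- 20% vs 40%: Φ[(0.20 − 1.960×0.10247)/0.10000] = Φ(−0.008) = 0.497.
- 10% vs 20%: Φ[(0.10 − 1.960×0.07984)/0.07906] = Φ(−0.715) = 0.237.

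| Assumed rates, 40 per group | Pooled formula | Exact chi-square |
|---|---|---|
| 20% vs 50% | 0.816 | 0.817 |
| 20% vs 40% | 0.497 | 0.497 |
| 10% vs 25% | 0.421 | 0.436 |
| 10% vs 20% | 0.237 | 0.247 |

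Fisher's exact test would give lower values. If all 50 per group were retained, the pooled formula gives 0.59 for 20% vs 40% and 0.286 for 10% vs 20%.

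Solving the same formula for 94% power at 40 per group gives an older-group rate of 27.6% against an assumed 1% in controls, 43.7% against 10%, 57.0% against 20% and 68.0% against 30%. The gap needed is therefore about 27 to 38 percentage points.

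**5. Ask how the composite's own power moves with its content.** By the plan's formula, 30% vs 60% (log odds ratio ln 3.5 = 1.2528, standard error 0.4725) gives Φ(2.652 − 1.960) = 0.755. At 30% vs 72%, where the odds ratio is still 6, it gives 0.953. The power depends on which events are on the list, and the list is what is missing.

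**The case against.** The strongest reply is that the plan does describe an analysis. The Sample size section sets out a logistic regression of a binary outcome on age group with a Wald test, and the Statistical analysis section only suggests tests by data type, so its list is not closed. This stands as far as it goes. A reader might infer that the powered comparison will never be run; the documents do not support that. They support the narrower statement that the comparison is described only as a power model, with an undefined response, and is not carried into the analysis section.

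It can also be said that the plan records the 24 to 28 outcomes and nowhere commits to a separate test of each at 0.05. That too is fair. A reader might want to count the false positives to be expected from so many tests. Such a count would rest on an unstated number of tests and on assumed event rates, since chi-square tests on rare events reject far less often than 5%. It forms no part of this point.

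A third reply is that the composite plainly means any listed outcome. The text does not say so, and mode of delivery, which is on the list, is not a poor outcome without further definition.

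Finally, this is an observational cohort with a broad aim. Even so, it states a hypothesis, an alpha and a power, and those need an endpoint.

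**Conclusion.** Wrong as written: the stated power attaches to no defined analysis. The 94% is correct for 20% vs 60% at 40 per group, but the outcome behind it is undefined and no primary outcome is named. For an individual listed outcome, power is about 50% at an assumed 20% vs 40% and about 25% at 10% vs 20% (chi-square, 40 per group). These rates are illustrative; the missing definition does not depend on them.

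Two further readings go beyond the documents. A reader might set the 60% against the Introduction's statement "Gestational DM and preeclampsia which increasing up to 10% in women more 40 years of age". That phrase may describe a rate or an increase, and it concerns women over 40, whereas the older group starts at 35. It also covers single conditions, so it says little about a composite of many. A reader might also conclude that the 20% and 60% have no basis. The source is named by author and year; its absence from the reference list is a bibliographic omission, and the documents alone cannot show whether it supports the rates.

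**What to change.** Before any outcome data are examined:

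- **Define the composite.** State the overall poor outcome as a fixed list of outcomes from the Investigations section, with the rule for combining them. Check that common events such as cesarean delivery or anemia do not push the expected rates well above 20% and 60%.
- **Support the rates.** Justify the expected rates for that list from earlier studies or historical hospital data, not from this study's data. Restate the power if they differ from 20% and 60%. Add the sizing study to the references.
- **Name the primary analysis.** Suggested wording for the Statistical analysis section: *The single primary outcome is the overall poor outcome (any of: [fixed list]), compared between women aged 35 or more and women aged 20–34 by logistic regression with a two-sided Wald test at 0.05. The 94% power applies only to this unadjusted comparison under rates of 20% and 60%. Individual outcomes, and the comparisons of 1A with 1B and of ART with spontaneous conception, are exploratory and reported with 95% confidence intervals.*
- **State the role of adjusted models.** The cohort is not randomised and admits ART conceptions, so the investigators should decide what part covariate-adjusted models play. They should not become exploratory by default.

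The cost is protocol wording and a look at published or historical rates; no new study data are needed. Claims on individual outcomes become more modest, and the stated power may fall if the defined list has a smaller gap. Naming one listed outcome as primary would also close the gap, but the study would then have to be re-sized for it.

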### **Statistical analysis**

Data will be entered and analyzed using IBM-SPSS software (IBM Corp. Released 2017. IBM SPSS Statistics for Windows, Version 25.0. Armonk, NY: IBM Corp.)

Qualitative data will be presented as Number and percent, Quantitative data will be tested for normality using Shapiro-Wilk's test then described as mean and standard deviation for normally distributed data and median and range for non-normally distributed. The appropriate statistical test will be applied according to data type with the following suggested tests: Chi-Square for categorical variable.

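### With 24 to 29 unranked outcomes, two age contrasts and no primary outcome or multiplicity rule, testing each at 0.05 puts the chance of a false age effect well above 5%

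*Combined protocol and SAP*

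**What the plan says.** The Aim of work covers maternal, obstetric, fetal and perinatal outcomes without ranking them. Section III, Investigations, itemises them, again unranked.

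The Sample size section sets up three contrasts:
- age 35 or more v 20-34 (50 women each);
- within the older group, 1A (35 to 40) v 1B (above 40), where "we will compare between the outcomes in the 2 groups which include maternal, obstetric, fetal and perinatal outcomes";
- mode of conception: "We will also compare between those with spontaneous pregnancy and those with ART".

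The sizing rests on one endpoint: "the authors hypothesize an overall poor outcome in 20% of young pregnant group vs. 60% in elderly pregnant group". For that endpoint the design "achieves 94% power at a 0.050 significance level to detect a change in Prob (Y=1) from the baseline value of 0.200 to 0.600", and "A two-sided Wald test is used". This is the only significance level in the document. The overall poor outcome is not defined there, and it does not reappear in Investigations or Statistical analysis.

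On testing, the Statistical analysis section says only: "The appropriate statistical test will be applied according to data type with the following suggested tests: Chi-Square for categorical variable". It gives no alpha, primary outcome, order of testing, adjustment or exploratory label.

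**The concern.** The sample size paragraph reads as a formal powered test, but the analysis section contains no test that corresponds to it. The plan instead leads to a page of p-values, one per outcome and contrast, all of equal standing. Some of those outcomes overlap: intrauterine fetal death with stillbirth, and, if the classes are tested separately, low with very low birth weight. One poor pregnancy can then appear as several findings that seem to corroborate each other.

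At stake is how a nominally significant age difference can be read. Without a designated test, a reader cannot know what share of the reported differences chance alone would be expected to produce. A primary outcome chosen after the results are seen would not repair this.

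**Working it through.** **1. The plan's own figure.** Inputs from Sample size: 40 per group, 20% v 60%, two-sided 0.05, Wald test.
- Odds ratio = (0.6/0.4)/(0.2/0.8) = 6.0, as stated; ln 6 = 1.792.
- SE = √[1/(40×0.2×0.8) + 1/(40×0.6×0.4)] = √(0.1563 + 0.1042) = 0.510.
- Power = Φ(1.792/0.510 − 1.960) = Φ(1.551) = 94.0%.
- Enrolment = 80/(1 − 0.20) = 100.

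Both figures reproduce. They describe one test of one outcome.

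**2. Counting the outcomes (Investigations).**

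| Domain | Items kept whole | Fluid disorders and birth-weight classes split | Early and late preterm also added |
|---|---|---|---|
| Obstetric | 7 | 8 | 8 |
| Maternal | 5 | 5 | 7 |
| Fetal | 4 | 4 | 4 |
| Perinatal | 8 | 10 | 10 |
| Total | 24 | 27 | 29 |

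**3. Nominal risk.** Assume that each outcome is tested at 0.05, that tests are independent, and that age affects no outcome. P(at least one false positive) = 1 − 0.95^m, and the expected number is 0.05m.

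| Outcomes | Main contrast | Both age contrasts |
|---|---|---|
| 24 | 70.8% (1.2 expected) | 91.5% (2.4) |
| 27 | 75.0% (1.35) | 93.7% (2.7) |
| 29 | 77.4% (1.45) | 94.9% (2.9) |

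**4. Why the nominal figures can be too high.** Rare outcomes cannot use up the full 5%, and the test matters. At 40 per group:
- Uncorrected chi-square cannot reject at 3 events v 0: 80×(3×40)²/(40×40×3×77) = 3.12, below 3.84. It rejects at 4 v 0: 80×(4×40)²/(40×40×4×76) = 4.21.
- Fisher's exact test gives p = 2×C(40,4)/C(80,4) = 0.116 at 4 v 0. It needs 6 v 0: 2×C(40,6)/C(80,6) = 0.026.

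**5. Allowing for this.** The documents give no event rates or subgroup sizes, so these are assumed: 27 outcomes; 50 v 50 (40 v 40 also checked for the main contrast); 1A v 1B at 25/25; correlation between outcomes from 0 to 0.5. In the mixed and rarer lists most rates lie between 0.2% and 15%, with a few common outcomes.

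| Assumed rates | Test | Main contrast | Both age contrasts |
|---|---|---|---|
| All 20% | Chi-square | 66-77% | 88-95% |
| Mixed | Chi-square | 57-62% | 75-81% |
| Rarer | Chi-square | 42-47% | 57-63% |
| All 20% | Fisher | 43-54% | 65-76% |
| Mixed | Fisher | 21-25% | 31-36% |
| Rarer | Fisher | 11-13% | 19-20% |

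Further checks of the main contrast under other assumed rates gave about 50-72% with uncorrected chi-square, and 15-51% with Fisher's test only where expected cells fall below 5. Taken together, with many rare outcomes the main-contrast risk is roughly 40-72% with uncorrected chi-square and 10-50% with Fisher's test for sparse tables or throughout.

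**6. After a fix.** One confirmatory test at 0.05 has a 5% false-positive risk and keeps 94% power for 20% v 60%. Bonferroni over 27 outcomes (0.05/27 = 0.00185) would cut that power to Φ(3.511 − 3.112) = 65%, or 72% with a pooled two-proportion formula. A single designated test is therefore the cheaper route.

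**The case against.** The strongest reply is that this is an observational cohort with a broad descriptive aim, and that adjusting many descriptive outcomes is a matter of judgement. That stands as far as mandatory adjustment goes: an exploratory label with intervals is enough. But the plan gives no such label, and its sizing paragraph presents a formal two-sided test.

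Three stronger readings are tempting, and the documents do not support them.
- *That the plan tests every outcome at 0.05.* A reader might infer this because no other level appears. The level is tied to the sizing test; the analysis section states none. The figures are therefore conditional on 0.05 being used.
- *That 81 tests (27 × 3) give a 98% chance of a false age effect.* ART v spontaneous is not an age contrast and cannot produce one. Its bullet also names no outcomes. The age family is about 54 tests.
- *That a false age effect is likely whatever is done.* Chi-square is only suggested, and the text calls for the appropriate test. At equal group sizes, fewer than 10 events in total gives expected cells below 5, where many analysts would use Fisher's test. The risk may then fall below one half.

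Three further points stand. we will compare between the outcomes in the 2 groups which include maternal, obstetric, fetal and perinatal outcomes sits in the 1A/1B bullet, so the main contrast rests on the aim, the group definitions and the sizing. The 27 count depends on splitting items that the text lists together. All the risks assume that age affects none of the outcomes, while the Introduction cites associations for many of them.

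**Conclusion.** The gap is real: there is no primary outcome, no significance level in the analysis section, and no hierarchy, adjustment or exploratory label for 24 to 29 outcomes in two age contrasts plus a conception contrast. If each outcome is tested at 0.05, the nominal risk of at least one false age effect is 71-77% in the main contrast and about 94% over both age contrasts (54 independent tests). With rare outcomes the main-contrast risk is lower: roughly 40-72% with uncorrected chi-square and 10-50% with Fisher's test for sparse tables or throughout. These ranges rest on assumed event rates, group splits and correlation. Whether a false finding is more likely than not depends on the test chosen; that the risk is well above 5% does not. This should be fixed. It does not undermine the stated power or enrolment.

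**What to change.** Before any outcome is compared:
1. Define the overall poor outcome from the components listed in Investigations.
2. State in Statistical analysis that its comparison between women aged 35 or more and those aged 20-34 is the single confirmatory test, at two-sided 0.05.
3. Report all other outcomes, and the 1A v 1B and ART v spontaneous contrasts, as exploratory, with estimates and 95% confidence intervals and no claims of significance.
4. If claims are wanted for the other older v younger outcomes, use Benjamini-Hochberg adjusted p-values with overlapping outcomes entered once. This is an option, not a necessity.

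The cost is wording, plus the work of defining the composite. N stays at 100 enrolled, and the 94% power is unchanged for the 20% v 60% that the sizing assumes. The downside is that some results with nominal p<0.05 can no longer be claimed as findings.
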